5.7.2 Secondary Efficacy Analysis

Summaries of change from baseline values will be reported at Visit 6 (after 8 weeks of treatment) for direct and total bilirubin, LDH, potassium, Hb and free haptoglobin using standard descriptive statistics for continuous variables with 95% CI of the mean by randomised treatment groups as described in Table 5 on the ITT population.

The analysis will be repeated on the PPS as well by actual treatment group and on mITT if applicable.

5.7.3 Exploratory Efficacy Analysis

Summaries of values and changes from baseline for each haemolysis marker (indirect, direct and total bilirubin, LDH, potassium, Hb and free haptoglobin) will be reported for each visit using standard descriptive statistics for continuous variables on the ITT population by randomised treatment groups as described in Table 5. Analyses will be repeated on the PPS by actual treatment group and on mITT if applicable.

Summaries of absolute and percent changes from baseline for indirect bilirubin, CHCM and MCHC will also be reported for each visit using the same approach.

Number and percentage of subjects who had at least 20% reduction in Indirect Bilirubin from baseline will be summarized at each post-baseline visit.

Number and percentage of subjects who had at least 5% reduction in CHCM and MCHC from baseline will be summarized at each post-baseline visit.

Analyses will be repeated on the PPS by actual treatment group and on mITT if applicable.

For each haemolysis marker, 3 figures will be provided:

- Line plots by subject: individual marker values (y-axis) in function of target visit day (x-axis) joined by subject and plotted in separate windows for the randomised cohorts (1, 2, 3, 4).
- Line plots by subject in log scale: same plot as previous with individual marker values displayed in a \log_{10} scale (y-axis)
- Means with 95% CIs of changes from baseline marker values for the 4 randomised cohorts (y-axis) in function of target visit day (x-axis). Means will be joined by group.

All graphics will be done on the ITT.

5.8 Safety Analyses

Safety evaluations will be performed using the safety set and analysed according to the analysis methods described in 5.1.1 unless specified otherwise. Missing values will not be imputed unless stated otherwise.

5.8.1 Adverse Events

AE data are collected from the time that ICF has been signed.

A treatment-emergent adverse event (TEAE) is defined as an AE that occurred or increased in severity on the same date or after the first dose of study medication.

A serious TEAE is defined as a serious adverse event (SAE) occurring or increasing in severity on the same date or after the first dose of study medication. An AE will be classified as related to study medication if the causality was recorded as certain, probable/likely and possible. An AE will be classified as unrelated to study medication if it was recorded as unlikely and unrelated. Additionally, AEs that have missing causality (after data querying) will be assumed to be related to study medication.

An AE leading to study discontinuation will be defined as an AE where the reason for study withdrawal was recorded as being due to this AE on the Study Termination CRF page or the response to Other Action taken on the Adverse Events CRF page, was recorded as early study termination.

An AE leading to treatment discontinuation is defined as an AE where the reason for treatment discontinuation was recorded as being due to this AE on the Treatment Termination CRF page or the action taken with study drug of the event was recorded as drug withdrawn on the Adverse Events CRF page.

AEs will be reported on a per-subject basis and per-event. On a per-subject basis, subjects with more than one AE overall or within a particular SOC/PT will be counted only once for that SOC/PT or overall. On a per-event basis (event counts), all severities of a same AE will be counted as only 1 AE. As, in CRF, every change in severity of a particular AE is recorded as a new AE log line and with a new AE number (the previous AE is reported with a resolved outcome and end date specified as the date the previous grade ended) a AE group number will be derived at time of analysis (regrouping all severities of a same AE) using the following rule:

- Any AE record with a start date on the day or 1 day after the stop date of another AE record of the same PT will be considered as a continuation of the previous AE and will have the same AE group number as the previous log line. AE group numbers with more than one record overall or within a particular SOC/PT will be counted as only 1 AE for that SOC/PT or overall in tables presenting AEs counts.

The imputation methods for completely or partially missing dates of AEs described in Section 5.1.9 will only be used to derive treatment emergence flag and to determine the day of the event relative to the first administration of study medication.

Only TEAEs will be tabulated. AEs that occurred during the study but before first IMP intake will be only listed on the Enrolled population.

The overall summary of TEAEs table will include the counts and percentage of subjects with at least 1 TEAE and the number of events with each of the following, tabulated on actual treatment:

- Any TEAEs
- Any TEAEs of severity ≥ 3
- Any TEAEs related to study medication
- Any TEAEs of severity ≥ 3 related to study medication
- Any TEAEs leading to discontinuation of study medication
- Any TEAEs leading to study discontinuation
- Any serious TEAEs
- Any serious TEAEs related to study medication
- Any TEAEs leading to death (outcome “fatal”)
- Any TEAEs leading to death related to study medication

The number and percentage of subjects reporting each TEAE and the count of number of events will be summarized by SOC and PT for the following types of TEAEs:

- All TEAEs
- TEAEs related to study medication
- TEAEs of severity ≥ 3 related to study medication
- Serious TEAEs
- TEAEs by maximum severity
- TEAEs by relationship to study medication

The SOC and PTs are to be sorted by decreasing order frequency of SOC and PTs in the overall subjects receiving VIT-2763.

For summaries by maximum severity, subjects with multiple TEAEs within a particular SOC/PT will be counted under the category of their most severe TEAE within that SOC/PT. TEAEs with missing severity will be counted in a missing category.

Listings of all AEs, all SAEs, all AEs leading to death, all AEs leading to treatment discontinuation, all AEs leading to study discontinuation and all AEs related to Study Drug with flag for AE within the treatment emergent period will be provided including relative day and duration of AE. Listings of all SAEs, all AEs leading to death and all AEs leading to treatment discontinuation will be specifically provided on safety set. Listings of all AEs will be provided on Enrolled population. Listings on all AEs leading to study discontinuation and all AEs related to Study Drug will be provided on the aITT.

Secondary Safety Endpoint

Secondary safety endpoint is the frequency and severity of reported or observed AEs by SOC and PTs using MedDRA coded terms, indicating seriousness criteria and relatedness over 8 weeks of treatment.

All TEAEs with a start date in the 88 days (corresponding to the target day 84 of the end of treatment visit plus the 4 days of visit window allowed in protocol) will be selected for this analysis. If missing start date, imputation method described in Section 5.1.9 will apply.

The number and percentage of subjects and the count of number of events reported in the 60 days after first dose of study treatment will be summarized by SOC and PT for the following types of TEAEs:

- All TEAEs
- TEAEs related to study medication
- Serious TEAEs
- TEAEs by maximum severity

The SOC and PTs are to be sorted by decreasing order frequency of SOC and PTs in the overall subjects receiving VIT-2763).

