8.6 EoT (or ET) Procedures/Visit 6 (Day 56±4 Days)

On completion of treatment (or if subject is discontinued/withdrawn early), assessments for Visit 6/Day 56±4 days (per Table 1) should be performed:

- Perform physical examination. Body systems to be assessed include general appearance, head (eyes, ears, nose, and throat), cardiovascular, respiratory, abdominal, musculoskeletal, neurological, lymph nodes, and skin
- Assess vital signs, e.g., systolic blood pressure, diastolic blood pressure, and pulse, after subject has rested for at least 5 minutes
- Record body weight
- Perform a single 12-lead ECG at pre-dose

- Assess SAEs/AEs
- Assess changes/additions to concomitant medications and treatments
- Prepare RBC blood smear (local laboratory) to assess for sickle cells (central laboratory)
- Urine pregnancy test (only in females of childbearing potential). Positive urine pregnancy test results need to be confirmed using a serum beta-hCG test (local laboratory assessment)
- Collect urinalysis samples for central laboratory assessment of:
 - pH, protein, glucose, ketone, RBCs, and WBCs (urinary dipstick test); quantitative measurement only if positive dipstick
 - Urinary microalbumin, creatinine, and microalbumin/creatinine ratio (spot urinary sample, morning void)
- Collect samples at pre-dose (trough) for central laboratory assessment of:
 - Haematology panel/RBC indices
 - Serum chemistry panel
 - Haemolysis markers
 - Endothelial inflammation/dysfunction markers
 - Total serum iron, serum ferritin, serum transferrin, calculated TSAT, hepcidin, and erythropoietin (central laboratory assessment)
- IMP administered, the morning dose on the visit day needs to be taken at site
- Perform a single 12-lead ECG at 2 hours (±30 minutes) post-morning dose
- Collect samples (2 hours post-morning dose) for total serum iron, serum ferritin, serum transferrin, calculated TSAT, hepcidin, and erythropoietin (central laboratory assessment)
- Record VOC episodes (number of events and pain intensity (NRS: 0-10) compared to historical VOC episodes). Assess visceral infarctions as per standard of care
- Collect the ASCQ-Me forms completed by subject
- Perform IMP accountability

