8.7 EoS (Follow-up) Procedures/Visit 7 (Day 84)

On completion of the study (Visit 7/Day 84±4 days), all assessments per Table 1 should be performed.

All subjects whether completing the treatment or who have withdrawn prematurely, will be followed up for 4 weeks (28±4 days after EoT) after their last administration of IMP to collect, at a minimum, any potential new AEs and concomitant medications (or other endpoints as defined in Table 1). If the Investigator has not seen the subject at in-hospital visit at the end of the reporting period, the Investigator must attempt 3 telephone calls to the subject, and if there is no response, the source documents and the eCRF should document the reason for study discontinuation as "lost to follow-up".

The following activities will be performed at Visit V7:

- Perform physical examination. Body systems to be assessed include general appearance, head (eyes, ears, nose, and throat), cardiovascular, respiratory, abdominal, musculoskeletal, neurological, lymph nodes, and skin
- Assess vital signs, e.g., systolic blood pressure, diastolic blood pressure, and pulse, after subject has rested for at least 5 minutes
- Perform a single 12-lead ECG
- Assess SAEs/AEs
- Assess changes/additions to concomitant medications
- Prepare RBC blood smear (local laboratory) to assess for sickle cells (central laboratory)
- Urine pregnancy test (only in females of childbearing potential). Positive urine pregnancy test results need to be confirmed using a serum beta-hCG test (local laboratory assessment)
- Collect urinalysis samples (urinary dipstick test) for central laboratory assessment of pH, protein, glucose, ketone, RBCs, and WBCs
- Collect samples for central laboratory assessment of:
 - Haematology panel/RBC indices
 - Serum chemistry panel
 - Haemolysis markers
 - Endothelial inflammation/dysfunction markers

- Total serum iron, serum ferritin, serum transferrin, calculated TSAT, hepcidin, and erythropoietin
- Record VOC episodes (number of events and pain intensity (NRS: 0-10) compared to historical VOC episodes). Assess visceral infarctions as per standard of care

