10.2 AE Reporting Period

The AE reporting period begins at the time the ICF is signed by the subject. The AE reporting period ends at the last study contact Visit 7/28±4 days after EoT.

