12.9 Safety Evaluations

All safety analyses will be performed on the safety set.

Adverse Events

Only TEAEs defined as events with an onset date later or on the same date as first IMP intake will be tabulated. AEs that occurred during the study but before first IMP intake will be only listed.

Summary tables with the counts and percentage of subjects and the number of events will be provided on overall subjects receiving VIT-2763, by dose group and on all subjects receiving placebo for any TEAEs, any severe TEAEs, any serious TEAEs, any TEAEs leading to study withdrawal and any TEAEs leading to death.

All AEs will be coded according to a standard dictionary (MedDRA).

Tables of the counts and percentages of subjects with at least 1 TEAE by SOC and PT will be provided for all TEAEs and TEAEs by severity and by relationship over 8 weeks of treatment (secondary endpoint) and up to 4 weeks after EoT. Similar tables will be provided for serious TEAEs, TEAEs leading to premature discontinuation of the study and TEAEs leading to death.

Clinical Laboratory Tests

Values by visit from baseline and changes from baseline by post-baseline visit for the haematologic, biochemistry, and urinalysis parameters will be summarised on overall subjects receiving VIT-2763, by dose group and on all subjects receiving placebo.

Shift tables crossing counts of baseline values lower, within and higher than laboratory normal range with the counts of each post-baseline visit will be provided for the haematologic, biochemistry, and urinallysis parameters on the same treatment groups.

Vital Signs and Body Weight

Values by visit from baseline and changes from baseline by post-baseline visit for blood pressure, pulse rate, and body weight will be summarised on overall subjects receiving VIT-2763, by dose group and on all subjects receiving placebo.

ECGs

Values by visit from baseline and changes from baseline by post-baseline visit for PR interval, QRS duration, QT interval, and QTcF interval will be summarised on overall subjects receiving VIT-2763, by dose group and on all subjects receiving placebo.

Abnormal ECG findings will be listed.

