2.6.2 Secondary Endpoint(s)

- Mean change from baseline in haemolysis markers as measured by direct and total bilirubin, LDH, potassium, Hb and free haptoglobin after 8 weeks of treatment.
- Frequency and severity of reported or observed adverse events (AEs) by system organ class (SOC) and preferred terms (PTs) using Medical Dictionary for Regulatory Activities (MedDRA) coded terms, indicating seriousness criteria and relatedness over 8 weeks of treatment.

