5.9.4 VOC Episode and Visceral Infarctions

The number of VOC episodes occurring over 8 weeks of treatment will be computed as the number of VOC episodes collected with a start date in the 60 days after baseline (corresponding to the target day 56 of the end of treatment visit plus the 4 days of visit window allowed in protocol).

The number of visceral infarctions occurring over 8 weeks of treatment will be computed as the sum of the number of visceral infarction collected at Visit 3, Visit 4, Visit 5 and Visit 6 (number of infarction since last visit collected at each visit in CRF).

Episodes counts will be categorized as:

- 0
- 1
- 2
- >2

Shift tables summarising the number of VOC episodes and the number of visceral infarctions in categories in the 8 weeks after baseline versus 8 weeks prior baseline will be provided.

The number of VOC episodes occurring over 4 weeks after end of treatment will be computed as the number of VOC episodes collected with a start date in the 28 days after treatment stop date.

The number of visceral infarctions occurring over 4 weeks after end of treatment will be the number of visceral infarction collected at Visit 7.

The number of VOC episodes occurring over 4 weeks after end of treatment, the number of visceral infarctions recorded at each visit and occurring over 4 weeks after end of treatment will be listed on the aITT. Each VOC episode with its pain intensity (NRS: 0-10) will be described by visit in a listing.

The ITT population will be used, and summaries will be repeated on the PPS as well.

5.9.5 *Pharmacokinetics Analyses*

Sparse sampling for determination of VIT 2763 plasma concentration following multiple dosing will be obtained from pre-dose trough to 2, 4 and 6 hours post-morning dose at study Visit 4 (V4).

The population pharmacokinetic analysis will be described in a separate analysis plan.

Pharmacokinetic plasma concentration of VIT-2763 will be summarised for the ITT and listed by subject for the aITT for each sampling time point by visit for cohorts 1, 2 and 3 (Placebo group not displayed), using descriptive statistics (including geometric mean and CV%, arithmetic mean, standard deviation, arithmetic CV%, median, maximum, minimum, and N). No formal statistical tests are planned.

The observed plasma concentration-time profiles will be plotted by subject using spaghetti plots for cohorts 1, 2 and 3.

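### SAP 5.8.1 gives two windows, 88 and 60 days, for adverse events over 8 weeks of treatment, and calls Day 84 the end of treatment visit

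*SAP*

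**What the plan says.** SAP 2.6.2 defines the secondary safety endpoint as the frequency and severity of adverse events, "indicating seriousness criteria and relatedness over 8 weeks of treatment". SAP 5.8.1, under Secondary Safety Endpoint, repeats that definition and then gives two time limits:

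- The selection sentence takes "All TEAEs with a start date in the 88 days (corresponding to the target day 84 of the end of treatment visit" with a 4-day visit window added), and says that these events are selected for this analysis.
- The tabulation sentence in the next paragraph summarises, by SOC and PT, subjects and "the count of number of events reported in the 60 days after first dose of study treatment".

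Elsewhere the documents place the visits as follows:

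- Protocol 8.6 is headed "EoT (or ET) Procedures/Visit 6 (Day 56±4 Days)" and Protocol 8.7 "EoS (Follow-up) Procedures/Visit 7 (Day 84)". The schedules of events in both documents and SAP Table 4 agree.
- SAP 5.9.4 sets a 60-day limit from baseline for VOC episodes over 8 weeks of treatment and explains that limit as "corresponding to the target day 56 of the end of treatment visit plus the 4 days of visit window allowed in protocol".
- Protocol 12.9 plans adverse event tables "over 8 weeks of treatment (secondary endpoint) and up to 4 weeks after EoT". SAP 2.6.3 makes the period to 4 weeks after end of treatment a separate exploratory endpoint.

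**The concern.** One endpoint has two windows that differ by 28 days, and the longer one is justified by giving the follow-up visit the name of the end of treatment visit. Two programmers working from SAP 5.8.1 could produce different tables under the same title.

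Safety and tolerability is the protocol's secondary objective, and this is the only adverse event endpoint at the secondary level. If the 88-day rule drives the tables, events from the off-drug follow-up are reported as events over 8 weeks of treatment. The secondary endpoint would then nearly duplicate both the exploratory summary and the unrestricted TEAE tables earlier in SAP 5.8.1, and the distinction that the protocol draws between on-treatment and follow-up events would be lost.

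The protocol cannot settle the matter by itself, because SAP section 1 gives the SAP precedence where the two differ. SAP 1.2 lists only additional analysis sets as changes from the protocol, so a longer adverse event window is not a declared change.

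**Working it through.** **Inputs**

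- Visit 6, end of treatment: Day 56±4, so Day 52 to Day 60 (Protocol Table 1 and 8.6; SAP Tables 3 and 4).
- Visit 7, end of study and follow-up: 28±4 days after end of treatment (Protocol Table 1, 4.2 and 8.7; SAP 2.2). Protocol 8.7 and SAP Table 4 also give it as Day 84±4.
- End of adverse event reporting: "The AE reporting period ends at the last study contact Visit 7/28±4 days after EoT" (Protocol 10.2).

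**The plan's two figures, reproduced**

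Window = target visit day + visit window.

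- 84 + 4 = 88. This is built on Visit 7, the follow-up visit.
- 56 + 4 = 60. This is built on Visit 6, the end of treatment visit, and is the derivation SAP 5.9.4 uses for VOC episodes over the same 8 weeks.

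Each figure follows from its own target day. Only 60 matches the end of treatment visit and the 8-week endpoint.

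**Size of the difference**

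- 88 − 60 = 28 days; 88/60 = 1.47; 28/88 = 32% of the longer window lies after Day 60.
- Days of the 88-day window that follow end of treatment: 88 − 52 = 36, 88 − 56 = 32 and 88 − 60 = 28, for end of treatment on Day 52, 56 and 60.

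**Extra observation time for completers with in-window visits**

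Visit 7 counted from end of treatment: earliest 52 + 24 = Day 76, target 56 + 28 = Day 84, latest 60 + 32 = Day 92. Read as Day 84±4, it falls on Day 80 to Day 88, which lies inside that range.

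Extra days = min(88, Visit 7 day) − 60:

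| Visit 7 on | Extra days | Relative to 60 |
|---|---|---|
| Day 76 | 16 | 16/60 = 27% |
| Day 80 | 20 | 20/60 = 33% |
| Day 84 | 24 | 24/60 = 40% |
| Day 88 or later | 28 | 28/60 = 47% |

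**Does 88 days reproduce the through-follow-up set?**

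Not exactly. Counted from end of treatment, adverse event reporting can run to Day 92, so an 88-day cut-off omits at most 92 − 88 = 4 days (Days 89 to 92). Read as Day 84±4, it omits none. The table above stops at Visit 7. SAE reporting runs on for 4 weeks after the last study visit (Protocol 10.7.2), so an SAE between an early Visit 7 and Day 88 would also be selected.

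All of these are calendar days. The documents give no adverse event rates, so they cannot be turned into event counts.

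**The case against.** The strongest reply is that the text resolves itself. The sentence that says what is tabulated gives 60 days; the 88-day sentence only picks a superset, and applied in the order written the 60-day limit governs. **This is a possible reading, and on it the tables are right.** It does not rescue the selection sentence: the 88-day step would then do nothing, the Day 84 label would still be wrong, and that sentence is where the start-date criterion and the missing-date imputation for this analysis are set.

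A second reply is that little turns on it. SAP 3.1 and 3.2 set no hypotheses or decision rules, unrestricted TEAE tables and listings with relative day are planned anyway, and this looks like a drafting slip rather than a chosen window. **All of that stands**, and it limits the harm to a mislabelled descriptive table.

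A third is that Visit 7 has two anchors in the documents, so the 16-day (27%) figure arises only when Visit 7 is counted from end of treatment. **That is so.** The upper limits, 28 extra days and at most Days 89 to 92 omitted, hold under either anchor.

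Last, SAP 5.1.2 makes the day of first dose Day 1, so 60 days after first dose could be read as reaching Day 61. **This is a fair refinement** and is taken up in the fix.

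**Conclusion.** The concern holds. SAP 5.8.1 gives two incompatible windows for one endpoint and wrongly names Day 84 as the end of treatment visit. The visit schedules, SAP 5.9.4 and the separation of periods in Protocol 12.9 all point to 60 days, so the 88-day selection sentence is the one in error.

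The effect depends on which sentence drives the tables, and the documents do not show how they were programmed. If the 60-day limit does, only the text is wrong. If the 88-day rule does, 16 to 28 further calendar days enter for completers with in-window visits (27% to 47% over 60 days), all off drug for a subject whose last dose is by Day 60. No test, sample size or safety record is affected. It should be fixed, because the endpoint's own definition is contradicted and the correction is small.

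**What to change.** In the selection sentence of SAP 5.8.1, Secondary Safety Endpoint, replace 88 days with 60 days after first dose, and replace target day 84 with target day 56, keeping the 4-day visit window. It then agrees with the tabulation sentence below it and with SAP 5.9.4. Adding that the window runs through study Day 60 removes the one-day ambiguity. Keep the through-follow-up tables separately, for the exploratory endpoint up to 4 weeks after end of treatment.

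The cost is one sentence in the SAP, a check of the table programs, and a re-run of the secondary safety tables only if they were programmed to 88 days.
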